1.1. Synopsis

Protocol Title:

A Study to Characterize the Time Course of Reversal of Opioid (Fentanyl)-Induced Respiratory Depression Following Administration of Nalmefene Autoinjector 1.5 mg (0.94% MgCl₂) Intramuscular and Narcan® 4 mg Intranasal in Healthy Subjects

Brief Title:

Pharmacodynamic Evaluation of Intramuscular Nalmefene Autoinjector 1.5 mg compared to Intranasal Narcan 4 mg

Rationale:

There are ethical challenges associated with conducting an efficacy study in the setting of opioid overdose using Nalmefene when life-saving, already-approved products are available, or to intentionally overdose subjects with opioids in a controlled setting in order to describe the onset of action and safety of Nalmefene.

In order to characterize the reversal onset of nalmefene, a pharmacodynamic evaluation of Nalmefene Autoinjector 1.5 mg (intramuscular) compared to Narcan 4mg (intranasal) has been designed.

Purdue has completed the conduct of a non-IND methods clinical study, [NAL9001](#), to develop and refine pharmacodynamic (PD) methods of assessing respiratory depression and other effects caused by an opioid (fentanyl) and clinical study [NAL1003](#) which utilized this opioid (fentanyl)-induced respiratory depression model.

In NAL1003, the onset and time course of nalmefene or naloxone antagonism of opioid agonist (fentanyl) induced respiratory effects was characterized. Nalmefene 1 mg, IM, anterolateral thigh; Naloxone 2 mg, IM, anterolateral thigh; and Narcan 4 mg, IN were administered following OIRD. Fentanyl was administered as a 3 step infusion, with a maximum total duration of 230 minutes to maintain steady state fentanyl concentrations once opioid-induced respiratory depression (OIRD) was reached with the 1st infusion. The duration of the fentanyl infusions was individualized (i.e., based on individual subjects rather than the entire cohort of subjects), based on ongoing assessments of minute ventilation measured to determine opioid effects and OIRD. Fentanyl, when co-administered with and without Nalmefene or Naloxone standard of care treatment, was found to be safe as employed in this model of OIRD. Taking into consideration the potency of nalmefene, the pharmacodynamic data suggest that Nalmefene 1 mg IM produced time to onset of reversal in minute ventilation comparable or better than Naloxone standard of care treatments.


 To characterize the time course (Magnitude of change in minute ventilation) of intramuscular naloxone and intranasal naloxone reversal from the opioid induced nadir 	
 Time to Onset (TTO) - Thresholds (X%) of reversal defined as X% of baseline reversal and calculated as X %) * (Baseline – OIRD) + OIRD, where X are 25, 33, 50, 67, 75, 90, and 100. Each Threshold % provides varying degrees of reversal.

Overall Design:

This will be a 2 part study. Part 1 is a Qualification Phase prior to Part 2 which will be conducted to identify subjects eligible to participate in the Treatment Phase. This will be based upon satisfying specified qualification criteria following completion of procedures and/or study drug administrations. Qualification may not be required if a subject has participated in previously conducted Clinical Studies ([NAL9001](#), [NAL1002](#), and [NAL1003](#)). Each Qualification cohort will have a screening, treatment, EOS and Follow-up. The qualification treatment phase will consist of 1 period and evaluate the pharmacodynamics (minute ventilation) of OIRD.

Qualification may be repeated if a subject has results that are uncertain regarding his or her suitability for Treatment (e.g., because of high variability or interference in minute ventilation, questionable equipment function/optimization, and/or other issues that render the data suboptimal).

Part 2 will be a single-center, randomized, 4 period crossover, 2 treatment replicate study to evaluate the pharmacodynamic effects (change in minute ventilation from opioid induced nadir (OIRD)) of nalmefene (1.5 mg) when given as an autoinjector intramuscularly (IM; into the thigh) compared to naloxone (Narcan 4 mg) when given intranasally (IN; into the nose) to reverse opioid (fentanyl) -induced respiratory depression (OIRD) in healthy subjects with prior opioid exposure. The Treatment Phase will have a screening, treatment, EOS and Follow-up.

Brief Summary:

This study is to determine the pharmacodynamics (change in minute ventilation) of nalmefene when given as an autoinjector intramuscularly (IM; into the thigh) compared to naloxone when given intranasally (IN; into the nose) to healthy subjects with prior opioid exposure under steady state fentanyl concentrations (opioid agonism).

Study details include:

- The study design graphic depicts the duration of each part.
- Part 1: Qualification Phase
 - Total study duration: up to approximately 40 days.
 - Subjects will be confined to the unit beginning the day prior to study drug administration (Check-in) in period 1 until End of Study (EOS) (or upon early discontinuation). Subjects who are ready for discharge on the same day as fentanyl administration should be required to have a ride home.
- Part 2: Treatment Phase
 - Total study duration: up to approximately 78 days.
 - Subjects will be confined to the unit beginning the day prior to study drug administration (Check-in) in period 1 until End of Study (EOS) (or upon early discontinuation). Subjects who are ready for discharge on the same day as fentanyl administration should be required to have a ride home.

Number of Participants:

Part 1: A sufficient number of subjects will be screened and entered into Part 1 to provide the number of subjects required in Part 2.

Part 2: A total of up to 22 subjects will be randomized to complete approximately 20.

In a non-inferiority test on MV at 5min from a 4 period, 2 treatment replicate cross-over design, a total sample size of 20 would achieve >90% power at a 2.5% significance level (1-sided) when the true difference between the means is 0.8L/min, the non-inferiority margin is -0.5L/min, and the within-subject standard deviation is 1.2L/min.

In a superiority test on MV at 5min from a 4 period, 2 treatment replicate cross-over design, a total sample size of 20 would achieve 83% power at a 2.5% significance level (1-sided) when the true difference between the means is 0.8L/min and the within-subject standard deviation is 1.2L/min.

The planned sample size is adequate for sequential testing of non-inferiority followed by superiority.

Study Population:

Part 1: Healthy male and female subjects with prior opioid exposure aged 18 to 55 years, inclusive, with no clinically significant medical history, who are deemed by the investigator suitable to take part in this clinical study.

Part 2: Qualified healthy male and female subjects with prior opioid exposure aged 18 to 55 years, inclusive, with no clinically significant medical history, who are deemed by the investigator suitable to take part in this clinical study.

Treatment Groups and Duration:

Test Treatment, Dose, and Mode of Administration

Part 1:

- Fentanyl citrate (up to approximately 650 mcg), IV, administered for up to 2 hours
 - Doses of fentanyl will be titrated to produce up to an average of 50% decrease in minute ventilation. Supplemental oxygen (up to 10 L/minute by simple mask) may be administered to prevent or treat a significant decrease in oxygen saturation. It is anticipated that the majority of subjects will be administered oxygen at a rate of 2 L/minute throughout the fentanyl administrations.

Part 2:

- Fentanyl citrate (up to approximately 1100 mcg in total), IV, administered for up to 230 minutes
 - Doses of fentanyl will be titrated to produce up to an average of 50% decrease in minute ventilation. Supplemental oxygen (up to 10 L/minute by simple mask) may be administered to prevent or treat a significant decrease in oxygen saturation. It is anticipated that the majority of subjects will be administered oxygen at a rate of 2 L/minute throughout the fentanyl administrations.
- Nalmefene Autoinjector 1.5 mg (0.94% MgCl₂), IM, anterolateral thigh
- Narcan 4 mg, IN; into the nose

[figure not shown]
Reference Treatment, Dose, and Mode of Administration:

Parts 1 and 2:

[figure not shown]
- Placebo (0.9% Sodium Chloride), IV

1.2. Schema

Part 1 Qualification Phase Study Design Graphic:

Part 2 Treatment Phase Study Design Graphic:

1.3. Schedule of Assessments

Table 1 Part 1 Study Flow Chart - Overall Procedures

Phase	Screening	Qualification			F/U	Notes
Period	Screening	Check-In	1	EOS	F/U	
Study Day	-57 - 2	-1	1	2	8-11	
Study Procedures						
Informed consent	X					
Medical history	X					Including drug and alcohol use history
Demography	X					Including weight, height, and BMI
Physical exam	X	X		X		At check-in: Symptom-directed, at discretion of investigator or designee
Inclusion/exclusion	X	X				
DSM-IV-TR (dependence)	X					
Clinical laboratory	X	X		X		Chemistry, hematology and urinalysis At check-in: chemistry and hematology testing only
Vital signs and SpO ₂ with HDYF?	X	X	X	X		Taken after 5 minutes seated (or during infusions when supine, seated, or semirecumbent): heart rate, blood pressure, respiratory rate, SpO ₂ Screening: Additional standing (for ~2 minutes) vital signs (heart rate and blood pressure) Obtained predose before saline infusion During fentanyl infusion: Predose, 30, and 60 minutes End of fentanyl infusion: end of infusion, 2 and 4 hrs. Time points may be added, omitted, or adjusted. Vital signs also taken pre- and post-naloxone challenge test.
Oral temperature	X	X	X	X		For safety purposes, forehead temperature may be substituted for oral. Days 1: Predose, and 8-12 hrs post infusion
Serum pregnancy test (females only)	X			X		
Serum FSH (post-menopausal females only)	X					
Urine pregnancy test (females only)		X				
Conventional 12-lead ECG	X	X		X		
Drug/alcohol screen	X	X				
Serology (HBsAg and HCV)	X					

Phase	Screening	Qualification			F/U	Notes
Period	Screening	Check-In	1	EOS	F/U	
Study Day Study Procedures	-57 --2	-1	1	2	8-11	
Naloxone challenge test		X				Performed at least approximately 12 hours prior to first dose in Period 1. Includes Objective Opioid Withdrawal Scale (OOVS). Does not need to be performed if conducted during a previous check-in visit within 60 days.
RVM/capnography/ PD training and practice session	X	X				May be performed at screening or Check-in day -1 or both.
Study drug dosing			X			Time = 0, relative to other procedures. [REDACTED]
Respiratory volume monitoring and capnography			X			Procedure will be performed pre (Baseline) and post IV study drug administration. Predose (baseline) and continuous RVM throughout dosing and for 15 minutes after the end of the infusion for remifentanil and for 1 hr after the end of the infusion for fentanyl. Time interval may be adjusted or separate time points may be examined.
Transcutaneous CO ₂ monitoring			X			Relative to fentanyl infusion, Predose (baseline) and continuous throughout dosing and for 1 hr after the end of the infusion for fentanyl. Time interval may be adjusted, or specific time points or multiple shorter intervals may be selected.
Continuous SpO ₂ monitoring			X			Relative to IV dosing: Predose to 8-12 hours for fentanyl Note: For fentanyl dosings, subjects can be taken off the pulse oximetry monitoring for up to a half hour each day to shower
Follow-up phone call					X	A follow-up phone call will be made to (or received from) each subject 7 to 10 days after Day 1 or after early withdrawal from the study.
Confined to study unit		↔				
Concomitant therapies		↔				
Adverse events		↔				

EOQ: End of Qualification; F/U: Follow-up; HYDF?=How do you feel question; IV=Intravenous; RVM= respiratory volume monitor(ing);
SpO₂=Hemoglobin-O₂ saturation determined by pulse oximetry

Table 2 Part 2 Study Flow Chart - Overall Procedures

Phase	Screen-ing	Treatment						F/U	Notes
Period	Screen-ing	Check-In	1	2	3	4	EOS	F/U	
Study Day	-57 --2	-1	1	4	7	10	11	18-21	
Study Procedures									
Informed consent	X								
Medical history	X								Including drug and alcohol use history
Demography	X								Including weight, height, and BMI
Physical exam	X	X				X			At check-in: Symptom-directed, at discretion of investigator or designee
Inclusion/exclusion	X	X							
DSM-IV-TR (dependence)	X								
Clinical laboratory	X	X				X			Chemistry, hematology and urinalysis At check-in: chemistry and hematology testing only Testing for COVID-19 may also be done at any time
Serum pregnancy test (females only)	X					X			
Serum FSH (post-menopausal females only)	X								
Urine pregnancy test (females only)		X							
Conventional 12-lead ECG	X	X				X			
Drug/alcohol screen	X	X							
Serology (HBsAg and HCV)	X								

Phase	Screening	Treatment						F/U	Notes
Period	Screening	Check-In	1	2	3	4	EOS	F/U	
Study Day	-57 --2	-1	1	4	7	10	11	18-21	
Study Procedures									
Naloxone challenge test		X							Performed at least approximately 12 hours prior to first dose in Period 1. Includes Objective Opioid Withdrawal Scale (OOWS). Does not need to be performed: 
 • If conducted during Part 1 and subject enters Part 2 within 60 days • If conducted on Day-1 of Part 2 within 60 days (eg. Backup subject not previously dosed).
Vital signs and SpO ₂ with HDYF?	X	X	X	X	X	X	X		Taken after 5 minutes seated (or during infusions when supine, seated, or semirecumbent): heart rate, blood pressure, respiratory rate, SpO ₂ Screening: Additional standing (for ~2 minutes) vital signs (heart rate and blood pressure) Days 1, 4, 7, 10: During fentanyl infusion: Predose (-15 minutes), end of infusion, 2 and 4 hrs post end of infusion. VS will also be performed on nondosing Days 2, 3, 5, 6, 8, and 9. Time points may be added, omitted, or adjusted. Vital signs also taken pre- and post-naloxone challenge test.
Oral temperature	X	X	X	X	X	X	X		For safety purposes, forehead temperature may be substituted for oral. Days 1, 4, 7, 10: Predose, and 8-12 hrs post infusion. Time points may be added, omitted, or adjusted.
Respiratory monitoring/PD training and practice session	X	X							May be performed at screening or Check-in Day -1 or both.
Randomization			X						Prior to study drug dosing in Period 1 only
Fentanyl Infusion administration			X	X	X	X			Time is relative to start of IV infusion. 3-step fentanyl infusion: first infusion at an initial rate of 5.0 mcg/min, a second infusion for 20 min and a third infusion up to 90 min. [REDACTED]

Phase	Screen-ing	Treatment						F/U	Notes
Period	Screen-ing	Check-In	1	2	3	4	EOS	F/U	
Study Day	-57 --2	-1	1	4	7	10	11	18-21	
Study Procedures									
Nalmefene or Naloxone Study drug dosing			X	X	X	X			Nalmefene or Naloxone will be administered approximately 10 min following the start of Fentanyl Infusion #2. Time = 0, relative to other procedures.
Local Tolerability			X	X	X	X	X		Nalmefene Treatment only, Days 1, 4, 7, 10: Prior to the start of IV infusion Relative to Nalmefene administration: 15, 30 minutes, 1 hr and 24 hr after nalmefene administration.
Blood sample for drug concentration			X	X	X	X			Relative to Nalmefene/Naloxone administration: 2.5, 5, 10, 15, 20, and 30 minutes and at 1, 2, 4, 8, 12, and 24 hours after nalmefene/naloxone administration.
Respiratory volume monitoring and capnography			X	X	X	X			Relative to fentanyl infusion, Predose (baseline) and continuous RVM throughout dosing and for 1 hr after the end of the infusion for fentanyl. Time interval may be adjusted, or specific time points or multiple shorter intervals may be selected.
Transcutaneous CO ₂ monitoring			X	X	X	X			Relative to fentanyl infusion, Predose (baseline) and continuous throughout dosing and for 1 hr after the end of the infusion for fentanyl. Time interval may be adjusted, or specific time points or multiple shorter intervals may be selected.
Continuous SpO ₂ monitoring			←-----→						Relative to fentanyl infusion: Predose to 8-12 hrs post dose Time interval may be adjusted, or specific time points or multiple shorter intervals may be selected dependent on the agonist administered. Note: Subjects can be taken off the pulse oximetry monitoring for up to a half hour each day to shower.
Device deficiencies			←-----→						
Follow-up phone call							X		A follow-up phone call will be made to (or received from) each subject 7 to 10 days after EOS or after early withdrawal from the study.

Phase	Screen-ing	Treatment						F/U	Notes
Period	Screen-ing	Check-In	1	2	3	4	EOS	F/U	
Study Day	-57 --2	-1	1	4	7	10	11	18-21	
Study Procedures									
Confined to study unit		◀-----►							
Concomitant therapies		◀-----►							
Adverse events		◀-----►							

EOS: End of study; F/U: Follow-up; HYDF?=How do you feel question; IV=Intravenous; RVM=respiratory volume monitor(ing);
SpO₂=Hemoglobin-O₂ saturation determined by pulse oximetry

OOWS	Objective Opioid Withdrawal Scale
PaCO ₂	arterial partial pressure of carbon dioxide
PCO ₂	partial pressure of CO ₂ in mm Hg (transcutaneous CO ₂)
PD	pharmacodynamics(s)
pH	negative log of hydrogen ion concentration
PI	principal investigator
PK	pharmacokinetic(s)
PO ₂	Partial pressure of oxygen
PPLP	Purdue Pharma Limited Partnership
PT	preferred term(s)
RBC	red blood cell (count)
ROU	healthy recreational opioid users
RR	respiratory rate
RVM	respiratory volume monitor(ing)
SAP	Statistical Analysis Plan
SAS	Statistical Analysis System
SC	subcutaneous
SGOT	serum glutamic-oxaloacetic transaminase (also AST)
SGPT	serum glutamate pyruvate transaminase (also ALT)
SoA	Schedule of Assessments
SOC	System Organ Class
SOP	Standard Operation Practices
SpO ₂	hemoglobin-O ₂ saturation determined by pulse oximetry

TCO2	transcutaneous CO2
THC	9-delta-tetrahydrocannabinol
TTO	time to onset
TV	tidal volume
uL	microliter(s)
ULN	upper limit of normal
US	United States
VAS	visual analog scale
WBC	white blood cell (count)
WHO	World Health Organization

1 Introduction

This statistical analysis plan (SAP) is designed to outline the statistical methods for the [NAL1004](#) study regarding test drug of fentanyl, naloxone, nalmefene and to assess the change in minute ventilation at 5 minutes of intramuscular nalmefene and intranasal naloxone reversal from the opioid induced nadir.

This document has been prepared based on [protocol Amendment 1](#) dated July 28, 2022. Details will be described in this analysis plan to ensure that the data listings, summary tables and figures which will be produced, and the statistical methodologies that will be used, are complete and appropriate to allow valid conclusions regarding the study objectives.

This analysis plan was finalized and approved by the sponsor [REDACTED] prior to the planned database lock.

This SAP supersedes the statistical considerations identified in the protocol; where considerations are substantially different, they will be identified, and justification will be provided. If additional analyses are required to supplement the planned analyses described in the SAP, they may be performed and will be identified in the clinical study report (CSR).

2 Study Design Overview

2.1 Overall Study Design

This will be a 2-part study. Part 1 is a Qualification Phase prior to Part 2 which will be conducted to identify subjects eligible to participate in the Treatment Phase. This will be based upon satisfying specified qualification criteria following completion of procedures and/or study drug administrations. Qualification may not be required if a subject has participated in Clinical Study [NAL1003](#). Each Qualification cohort will have a screening, treatment, EOS and Follow-up. The qualification treatment phase will consist of 1 period and evaluate the pharmacodynamics (minute ventilation) of OIRD.

Part 2 will be a single-center, randomized, 4 period crossover, 2 treatment replicate study to evaluate the pharmacodynamic effects (change in minute ventilation from opioid induced nadir (OIRD)) of nalmefene (1.5 mg) when given as an autoinjector intramuscularly (IM; into the thigh) compared to naloxone (Narcan 4 mg) when given intranasally (IN; into the nose) to reverse opioid (fentanyl) -induced respiratory depression (OIRD) in healthy subjects with prior opioid exposure. The Treatment Phase will have a screening, treatment, EOS and Follow-up.

The two treatment sequences for first 2 periods:

- Sequence 1: Narcan 4 mg, IN - Nalmefene Autoinjector 1.5 mg, IM
- Sequence 2: Nalmefene Autoinjector 1.5 mg, IM - Narcan 4 mg, IN

[Table 1](#) and [Table 2](#) below present the complete schedule of activities for NAL1004.

Table 1 Part 1 Study Flow Chart - Overall Procedures

Phase	Screening	Qualification			F/U	Notes
Period	Screening	Check-In	1	EOS	F/U	
Study Day	-29 - -2	-1	1	2	8-11	
Study Procedures						
Informed consent	X					
Medical history	X					Including drug and alcohol use history
Demography	X					Including weight, height, and BMI
Physical exam	X	X		X		At check-in: Symptom-directed, at discretion of investigator or designee
Inclusion/exclusion	X	X				
DSM-IV-TR (dependence)	X					
Clinical laboratory	X	X		X		Chemistry, hematology and urinalysis At check-in: chemistry and hematology testing only
Vital signs and SpO ₂ with HDYF?	X	X	X	X		Taken after 5 minutes seated (or during infusions when supine, seated, or semirecumbent): heart rate, blood pressure, respiratory rate, SpO ₂ Screening: Additional standing (for ~2 minutes) vital signs (heart rate and blood pressure) Obtained predose before saline infusion During fentanyl infusion: Predose, 30, and 60 minutes End of fentanyl infusion: end of infusion, 2 and 4 hrs. Time points may be added, omitted, or adjusted. Vital signs also taken pre- and post-naloxone challenge test.
Oral temperature	X	X	X	X		For safety purposes, forehead temperature may be substituted for oral. Days 1: Predose, and 8-12 hrs post infusion
Serum pregnancy test (females only)	X			X		

Phase	Screening	Qualification			F/U	Notes
Period	Screening	Check-In	1	EOS	F/U	
Study Day	-29 --2	-1	1	2	8-11	
Study Procedures						
Serum FSH (post-menopausal females only)	X					
Urine pregnancy test (females only)		X				
Conventional 12-lead ECG	X	X		X		
Drug/alcohol screen	X	X				
Serology (HBsAg and HCV)	X					
Naloxone challenge test		X				Performed at least approximately 12 hours prior to first dose in Period 1. Includes Objective Opioid Withdrawal Scale (OOVS). Does not need to be performed if conducted during a previous check-in visit within 60 days.
RVM/capnography/ PD training and practice session	X	X				May be performed at screening or Check-in day -1 or both.
Study drug dosing			X			Time = 0, relative to other procedures. [REDACTED]
Respiratory volume monitoring and capnography			X			Procedure will be performed pre (Baseline) and post IV study drug administration. Predose (baseline) and continuous RVM throughout dosing and for 15 minutes after the end of the infusion for remifentanil and for 1 hr after the end of the infusion for fentanyl. Time interval may be adjusted or separate time points may be examined.
Transcutaneous CO ₂ monitoring			X			Obtained prior to the start of the saline infusion, every 15 minutes during saline infusion and at the end of the saline infusion, every 5 minutes during the fentanyl Infusion, and at the end of the fentanyl Infusion. Time points may be added and adjusted.

Phase	Screening	Qualification			F/U	Notes
Period	Screening	Check-In	1	EOS	F/U	
Study Day	-29 - -2	-1	1	2	8-11	
Study Procedures						
Continuous SpO ₂ monitoring			X			Relative to IV dosing: Predose to 8-12 hours for fentanyl Note: For fentanyl dosings, subjects can be taken off the pulse oximetry monitoring for up to a half hour each day to shower
Follow-up phone call					X	A follow-up phone call will be made to (or received from) each subject 7 to 10 days after Day 1 or after early withdrawal from the study.
Confined to study unit		◀-----►				
Concomitant therapies	◀-----►					
Adverse events	◀-----►					

EOQ: End of Qualification; F/U: Follow-up; HYDF?=How do you feel question; IV=Intravenous; RVM= respiratory volume monitor(ing);

SpO₂=Hemoglobin-O₂ saturation determined by pulse oximetry

Table 2 Part 2 Study Flow Chart - Overall Procedures

Phase	Screen-ing	Treatment						F/U	Notes
Period	Screen-ing	Check-In	1	2	3	4	EOS	F/U	
Study Day	-29 --2	-1	1	4	7	10	11	18-21	
Study Procedures									
Informed consent	X								
Medical history	X								Including drug and alcohol use history
Demography	X								Including weight, height, and BMI
Physical exam	X	X					X		At check-in: Symptom-directed, at discretion of investigator or designee
Inclusion/exclusion	X	X							
DSM-IV-TR (dependence)	X								
Clinical laboratory	X	X					X		Chemistry, hematology and urinalysis At check-in: chemistry and hematology testing only Testing for COVID-19 may also be done at any time
Serum pregnancy test (females only)	X						X		
Serum FSH (post-menopausal females only)	X								
Urine pregnancy test (females only)		X							
Conventional 12-lead ECG	X	X					X		
Drug/alcohol screen	X	X							

Phase	Screening	Treatment						F/U	Notes
Period	Screening	Check-In	1	2	3	4	EOS	F/U	
Study Day	-29 --2	-1	1	4	7	10	11	18-21	
Study Procedures									
Serology (HBsAg and HCV)	X								
Naloxone challenge test		X							Performed at least approximately 12 hours prior to first dose in Period 1. Includes Objective Opioid Withdrawal Scale (OOWS). Does not need to be performed if conducted during Part 1 and subject enters Part 2 within 60 days
Vital signs and SpO ₂ with HDYF?	X	X	X	X	X	X	X		Taken after 5 minutes seated (or during infusions when supine, seated, or semirecumbent): heart rate, blood pressure, respiratory rate, SpO ₂ Screening: Additional standing (for ~2 minutes) vital signs (heart rate and blood pressure) Days 1, 4, 7, 10: During fentanyl infusion: Predose (-15 minutes), end of infusion, 2 and 4 hrs post end of infusion. Time points may be added, omitted, or adjusted. Vital signs also taken pre- and post-naloxone challenge test.
Oral temperature	X	X	X	X	X	X	X		For safety purposes, forehead temperature may be substituted for oral. Days 1, 4, 7, 10: Predose, and 8-12 hrs post infusion. Time points may be added, omitted, or adjusted.
Respiratory monitoring/PD training and practice session	X	X							May be performed at screening or Check-in Day -1 or both.
Randomization			X						Prior to study drug dosing in Period 1 only

Phase	Screen-ing	Treatment						F/U	Notes
Period	Screen-ing	Check-In	1	2	3	4	EOS	F/U	
Study Day	-29 --2	-1	1	4	7	10	11	18-21	
Study Procedures									
Fentanyl Infusion administration			X	X	X	X			Time is relative to start of IV infusion. 3-step fentanyl infusion: first infusion at an initial rate of 5.0 mcg/min, a second infusion for 20 min and a third infusion up to 90 min, see Table 7 .
Nalmefene or Naloxone Study drug dosing			X	X	X	X			Nalmefene or Naloxone will be administered approximately 10 min following the start of Fentanyl Infusion #2. Time = 0, relative to other procedures.
Local Tolerability			X	X	X	X	X		Nalmefene Treatment only, Days 1, 4, 7, 10: Prior to the start of IV infusion Relative to Nalmefene administration: 15, 30 minutes, 1 hr and 24 hr after nalmefene administration.
Blood sample for drug concentration			X	X	X	X			Relative to Nalmefene/Naloxone administration: 2.5, 5, 10, 15, 20, and 30 minutes and at 1, 2, 4, 8, 12, and 24 hours after nalmefene/naloxone administration.
Respiratory volume monitoring and capnography			X	X	X	X			Relative to fentanyl infusion, Predose (baseline) and continuous RVM throughout dosing and for 1 hr after the end of the infusion for fentanyl. Time interval may be adjusted, or specific time points or multiple shorter intervals may be selected.
Transcutaneous CO ₂ monitoring			X	X	X	X			Relative to fentanyl infusion, Predose (baseline) and continuous throughout dosing and for 1 hr after the end of the infusion for fentanyl. Time interval may be adjusted, or specific time points or multiple shorter intervals may be selected.

Phase	Screen-ing	Treatment						F/U	Notes
Period	Screen-ing	Check-In	1	2	3	4	EOS	F/U	
Study Day	-29 --2	-1	1	4	7	10	11	18-21	
Study Procedures									
Continuous SpO ₂ monitoring									Relative to fentanyl infusion: Predose to 8-12 hrs post dose Time interval may be adjusted, or specific time points or multiple shorter intervals may be selected dependent on the agonist administered. Note: Subjects can be taken off the pulse oximetry monitoring for up to a half hour each day to shower.
Device deficiencies									
Follow-up phone call							X		A follow-up phone call will be made to (or received from) each subject 7 to 10 days after EOS or after early withdrawal from the study.
Confined to study unit									
Concomitant therapies									
Adverse events									

EOS: End of study; F/U: Follow-up; HYDF?=How do you feel question; IV=Intravenous; RVM=respiratory volume monitor(ing);

SpO₂=Hemoglobin-O₂ saturation determined by pulse oximetry

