5.3 Eligible Analysis Set (EAS)

Twenty subjects will be expected to complete the study, each of whom will receive nalmefene or naloxone in different order after fentanyl -induced respiratory depression (OIRD).

For each period, eligible analysis set (EAS) include subjects/periods who are randomized, receive study drug, have at least 1 valid PD measurement, and their OIRDs are worse than baseline for MV and TCO₂. Note: baseline and OIRD for MV and TCO₂ may be different. Therefore, eligible analysis set for each PD parameter and period may be different.

To evaluate the treatment difference between nalmefene and naloxone, the same treatment under different periods will be pooled by averaging PD parameters from eligible data for each subject.

This analysis set will be used as primary analysis.

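### The SAP text gives treatment order only for Periods 1–2 and averages replicates with no period or sequence term, so period effects in the 5-minute reversal go unadjusted, at a cost in power and, with imbalance, some bias

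*SAP*

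**What the plan says.** The protocol synopsis and SAP 2.1 both describe Part 2 as a "randomized, 4 period crossover, 2 treatment replicate study". SAP 2.1 introduces the order with "The two treatment sequences for first 2 periods" and gives two lines: "Sequence 1: Narcan 4 mg, IN - Nalmefene Autoinjector 1.5 mg, IM" and "Sequence 2: Nalmefene Autoinjector 1.5 mg, IM - Narcan 4 mg, IN". The text gives no order for Periods 3 and 4 and no allocation ratio. Table 2 of the SAP places randomisation "Prior to study drug dosing in Period 1 only", so no second randomisation is described.

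For the analysis, SAP 5.3 says that "the same treatment under different periods will be pooled by averaging PD parameters from eligible data for each subject", and SAP 5.4 repeats this for the full analysis set. Eligibility is judged period by period: "eligible analysis set for each PD parameter and period may be different". SAP 6.2 and 6.2.1 give the two hypotheses (margin -0.5, then 0) and the one-sided 0.025 level. SAP 9.2 presents the 5-minute change by treatment with a 95% confidence interval. None of these sections names a model, a period effect or a sequence effect.

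The Part 2 design graphic (protocol 1.2) is not shown in the text reviewed and may contain the full order.

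**The concern.** In a crossover, period effects are normally removed by modelling period, or by using the randomised sequence in the analysis. Here the replicates are collapsed to one mean per treatment per subject, and the period information is lost before the comparison is made. What happens to a period effect then depends on three things that the text leaves open: the order in Periods 3 and 4, the number of completers in each sequence, and which single periods are ineligible.

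Some change across periods is possible. Each subject has four fentanyl titrations, on Days 1, 4, 7 and 10. What is at stake is mainly power for superiority, where the stated 83% leaves little room. There is also some bias in the nalmefene-minus-Narcan estimate if the sequences are unequal or not complementary.

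**Working it through.** **Inputs from the documents** (SAP 2.2, 6.2.1): N = 20 completers of up to 22 randomised; true difference 0.8 L/min; within-subject SD 1.2 L/min; margin -0.5 L/min; one-sided alpha 0.025.

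**Assumptions** (not in the documents): linear drift in the 5-minute reversal of d = 0, 0.25 or 0.5 L/min per period; the order in Periods 3–4; the split of completers between sequences.

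**The plan's own figure.** A subject's difference between two-replicate means has variance 2 × 1.2²/2 = 1.44, so SD 1.2. The standard error is 1.2/√20 = 0.268. With the noncentral t distribution, superiority power is 82.8% on 38 error degrees of freedom and 83.4% on 56, which reproduces the stated 83%. Non-inferiority power is above 99%, consistent with the stated >90%. A paired t-test on subject averages (19 df) gives 80.7%. The stated 83% thus fits a period-level error term better than the averaging in SAP 5.3.

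**Effect of drift on one complete subject.** Write R for Narcan, T for nalmefene, and p1 to p4 for the period effects 0, d, 2d, 3d.

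- Repeated order RTRT: (p2 + p4 - p1 - p3)/2 = (d + 3d - 0 - 2d)/2 = +d. TRTR gives -d.
- Mirrored order RTTR: (p2 + p3 - p1 - p4)/2 = (d + 2d - 0 - 3d)/2 = 0. TRRT also gives 0.
- Same Period 3–4 order for everyone (RTRT with TRRT): +d and 0, mean +0.5d at equal split. With TR for everyone it is -0.5d.

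**Repeated order, mean bias** = d × (n1 - n2)/(n1 + n2), with n1 on Narcan first. At 10/10 it is 0. At 9/11 and d = 0.5 it is 0.5 × (-2)/20 = -0.05 L/min.

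**Repeated order, error at 10/10.** The ±d split adds about (20/19) × d² to the variance. At d = 0.5 this is 1.44 + 0.263 = 1.703, SD 1.305, and the standard error becomes 1.305/√20 = 0.292 instead of 0.268.

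**Simulation**, repeated order. The unadjusted test is a paired t-test on averages; the adjusted test adds a sequence factor with equal weight for each sequence.

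| Split | d | Superiority power, unadjusted | Adjusted | Type I error at -0.5, unadjusted |
|---|---|---|---|---|
| 10/10 | 0 | about 80.7% | about 80.5% | 2.5% |
| 10/10 | 0.25 | about 79% | about 80.5% | about 2.2% |
| 10/10 | 0.5 | about 75% | about 80% | 1.7% |
| 9/11 | 0.25 | about 77% | about 80% | below 2.5% |
| 9/11 | 0.5 | about 70% | about 80% | below 2.5% |
| 11/9 | 0.25 | about 82% | about 80% | 2.8% |
| 11/9 | 0.5 | about 81% | about 80% | 2.6% |
| 12/8 (stress case) | 0.5 | about 85%, raised by bias of +0.10 | about 79% | 3.9% |
| 8/12 (stress case) | 0.5 | about 64% | about 79% | below 2.5% |

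Non-inferiority power was at least 98% in every repeated-order setting.

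**Other routes to bias.**

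- Same Period 3–4 order for everyone, d = 0.5, 10/10: bias +0.25 or -0.25 L/min, giving type I error of about 13% or superiority power of about 48%. A sequence factor does not remove this.
- One ineligible period: a mirrored subject is then shifted by 0.5d to 1.5d in size. For example, RTTR without Period 1 gives (d + 2d)/2 - 3d = -1.5d. A repeated-order subject is shifted by 0 or by 2d.
- A step of size s after Period 1 shifts a mirrored subject by ±0.5s, so mirroring protects only against linear drift.

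**The case against.** The strongest reply is that little harm need follow. With complementary sequences of equal size, drift cancels from the mean difference without any adjustment, and the unadjusted test is conservative. If allocation were 11:11 and 20 of 22 completed, only 10/10, 11/9 or 9/11 could occur, and type I error then stays close to 2.5% or below. Non-inferiority is barely affected. All of this stands.

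The drift is also assumed, and 0.5 L/min per period is large: 3 × 0.5 = 1.5 L/min from Period 1 to Period 4, nearly twice the assumed treatment difference. The endpoint is a change from the same period's OIRD value, so a shift in the general level of MV drops out; only a change in the reversal itself matters. Fentanyl is titrated to an MV target, and the training session comes before Period 1. These points make large drift less likely but do not exclude a period effect, and checking for one is why period is normally modelled.

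The order may be in the design graphic. If so, the gap in SAP 2.1 is one of wording. The unadjusted averaging in SAP 5.3 remains.

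A reader might infer that drift must bias the primary difference, or that type I error is generally inflated. The documents do not support this: it takes unequal sequences, excluded periods or non-complementary sequences. Nor do they show that the order of Periods 3–4 was left undecided, only that the text does not state it.

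**Conclusion.** The point holds as a weakness of the analysis method, of moderate size. The text averages replicates and names no period or sequence term, so a period effect in the 5-minute reversal is not removed.

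Under a repeated order and an assumed d = 0.5, the cost is about 5 points of superiority power at 10/10. At 9/11 it is about 10 points, with a bias of -0.05 L/min. At d = 0.25 and 10/10 it is about 1 point, and at d = 0 there is none. Type I error is not a material problem at the splits expected under balanced allocation; the 3.9% at 12/8 is a stress case. Larger bias would need period-level exclusions or the same Period 3–4 order in both sequences. The text does not rule out either, and it does not show that either occurs.

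**What to change.** In SAP 9.2, replace the unadjusted comparison of averaged replicates with a period-level mixed model for change in MV from OIRD at 5 minutes. Use treatment, period and sequence as fixed effects and subject as random. Test -0.5 and then 0 on its treatment contrast. This uses each eligible period as observed and so also copes with single-period exclusions under SAP 5.3.

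In SAP 2.1, state the full four-period sequences and a balanced allocation. The sequences must be complementary, either mirrored (RTTR/TRRT) or alternating (RTRT/TRTR). Once period is in the model, the choice between the two matters little. If both sequences shared one Period 3–4 order, treatment and period could not be separated in those periods.

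The model costs a few degrees of freedom. A sequence factor on subject-level differences is a simpler alternative, but only for complementary sequences and complete subjects. With no drift it costs about 0.3 points of power at 10/10 and about 2 points at 12/8. Stating the sequences costs nothing.
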